3.6.2.9 Clinical Laboratory Test Values

Summary statistics and plots will be generated for the change from baseline values, as deemed clinically appropriate. Summary statistics for the raw laboratory safety tests, may also be computed, as deemed clinically appropriate.

3.6.3 Determination of Sample Size

No formal sample size calculation is provided as the purpose of this trial is exploratory. Up to twelve patients will be randomized, 6 to each trial arm. If this randomization rate is not achieved in a reasonable timeframe, the Sponsor will review the required sample size.

3.7 Data Quality Assurance

The clinical research center will be monitored by the trial monitor to ensure correct performance of the trial procedures and assure that the trial will be conducted according to the relevant regulatory requirements.

By signing this protocol, the Sponsor agrees to be responsible for implementing and maintaining quality control and quality assurance systems with written procedures to ensure that trials are conducted, and data are generated, documented, and reported in compliance with the protocol, accepted standards of GCP and all applicable federal state and local laws, rules and regulations relating to the conduct of the clinical trial.

Regulatory authorities, the IRB/IEC and/or the Sponsor may request access to all source documents, eCRFs, and other trial documentation for on-site audit or inspection. Direct access to these documents must be guaranteed by the Investigator, who must always provide support for these activities.

4. ETHICS

4.1 Regulatory and Ethical Considerations

The Investigator must promptly supply the Sponsor or its designee, the IRB/ IEC, competent authorities and, where applicable, the Trial Center, with written reports on any changes significantly affecting the conduct of the trial or increasing the risk to patients.

This trial will be conducted in accordance with the protocol and:

- Consensus ethical principles derived from international guidelines including the Declaration of Helsinki and Council for International Organizations of Medical Sciences (CIOMS) International Ethical Guidelines.
- Applicable International Conference on Harmonization (ICH) GCP Guidelines.
- Regulation (EU) No 536/2014.
- Applicable laws and regulations.

The protocol, substantial protocol amendments, ICF, IB, and other relevant documents (e.g., any other written information regarding this trial to be provided to the patient or the patient's legal representative) must be submitted to the competent authorities and IRB/IEC and reviewed and approved by both institutions prior to being used in the trial, except for changes necessary to eliminate an immediate hazard to trial patients.

The Investigator will be responsible for the following:

- Providing written summaries of the progress and status of the trial to the IRB/IEC annually or more frequently in accordance with the requirements, policies, and procedures established by the IRB/IEC.
- Overall conduct of the trial at the site and adherence to requirements of ICH guideline for good clinical practice (E6(R2)) and applicable laws including but not limited to GDPR and applicable German privacy laws.
- Submitting reports of SAEs according to the timeline and method outlined in the protocol.
- Obtaining all required patient consents in accordance with applicable laws.

The Sponsor will cover this trial by means of an adequate insurance of the participating patients which will be in place prior to the start of the trial. As per local regulations, details about the insurance are described in the patient information sheet and informed consent form. A copy of the insurance certificate is filed in the Investigator Site File and the patient can request a copy.

4.2 Patient Information and Consent

All parties will ensure protection of patient personal data according to GDPR (and applicable German privacy laws) and will not include patient names on any forms, reports, publications, or in any other disclosures, except where required by laws.

The informed consent document used in this trial, and any changes made during the course of the trial, must be prospectively approved by the IRB/EC.

The investigator, or a person designated by the investigator, will obtain written informed consent from each patient before any trial specific activity is performed. The investigator and patient will each retain an original of the duly (by investigator and patient) signed ICF.

Prior to execution of the clinical trial, the Sponsor works together with the investigator to prepare the written ICF and other written information investigator. The written ICF and any other written information will be submitted to the competent authority according to the local requirements.

- The investigator is responsible for explaining the nature and purpose of the trial as well as other trial related matters to patients, using the written information. Also, the investigator is responsible for obtaining the patient's full understanding and written consent to participate in the trial of their own free will.
- The investigator or other responsible personnel who provided explanations (including collaborators who gave supportive information, if applicable) and the patient should sign and date the written information or write down his/her name and date the form.
- ICF must be obtained by the time that the first observations/examinations of the pre-investigational period are performed.
- The investigator or other responsible personnel should note the following when obtaining ICF from patients:
 - No patient may be subjected to undue influence, such as compulsory enrolment into a trial.

- The language and expressions used in the ICF should be as plain and understandable as possible. Patients should be given the opportunity to ask questions and receive satisfactory answers to the inquiry and should have adequate time to decide whether to participate in the trial. Written information should not contain any language or contents that causes the patients to waive or appears to waive any legal rights or that releases/mitigates or appears to release/mitigate the trial site, the investigator, collaborators, or the Sponsor from liability for negligence.

4.3 Data Protection

- Trial patients will be assigned a unique trial patients identification number. Any trial patients' records or datasets that are transferred to the Sponsor will contain this identifier only; trial patients names and any information which would make the trial patients identifiable will not be transferred. All laboratory specimens, evaluation forms, reports, and other records will be identified in a manner designed to maintain trial patients' confidentiality.
- The trial patients must be informed that the patients' personal trial-related data will be used by the Sponsor in accordance with applicable data protection laws as stated in the ICF. The level of disclosure must also be explained to the trial patients as well as the patients' rights including the right to access or erase his/her personal data.
- The trial patients must be informed that the patients' medical records may be reviewed by Clinical Quality Assurance auditors or other authorized personnel appointed by the Sponsor, by appropriate IRB/IEC members, and by inspectors from regulatory authorities.
- All records will be kept in a secure storage area with limited access.

4.4 Patient Confidentiality

Individual patient medical information obtained because of this trial is considered confidential and disclosure to third parties is prohibited. Such medical information may be given only after approval of the patient to the patient's physician or to other appropriate medical personnel responsible for the patient's well-being.

The Sponsor, its board members, and its personnel shall not disclose any confidential information on patients obtained during the performance of their duties in the clinical trial without justifiable reasons. All individuals and organizations involved in the trial must pay very careful attention to protect patients' privacy with appropriate measures, for example, by prohibiting the use of any private information that may identify a patient (e.g., name or address). These details shall be processed in accordance with GDPR and the applicable local and regional laws.

Even though any individuals involved in the trial, including the trial monitors and auditors, may get to know matters related to patients' privacy due to direct access to source documents, or from other sources, they may not disclose the content to third parties other than those designated by the Sponsor.

5. DOCUMENTATION

5.1 Archiving

Unless other Union law requires archiving for a longer period, the Sponsor and the Principal Investigator shall archive the content of the clinical trial master file for at least 25 years after the end of the clinical trial. However, the medical files of subjects shall be archived in accordance with national law.

5.2 Recording of Data in Source Documents and eCRFs

Wherever possible, all data will be entered directly into the eCRFs. In some cases, source documents will be used.

A Data Management Plan will be written by the Sponsor or delegate which will be finalized prior to the first dosing.

6. CONFIDENTIALITY AND PUBLICATION POLICY

By signing this protocol, the Principal Investigator reaffirms to the Sponsor that the Investigator will maintain in confidence all information furnished to the Investigator or resulting from this trial. The Investigator will only divulge such information as may be necessary to the IRB/IEC and the members of the staff and the patients who are involved in this trial.

The Sponsor supports publication of the trial results, regardless of the outcome. It is understood that all data related to the trial remains the sole and exclusive property of the Sponsor. The Trial Center and/or Investigator may publish the results from the Trial; provided, however, that the Trial Center and/or Investigator submits the proposed publication to the Sponsor for review at least sixty (60) days prior to the date of the proposed publication. The Sponsor shall have the right to request modifications or removal from the proposed publication any Sponsor Information. The Trial Center and/or Investigator shall remove such Sponsor Information from the publication but only to the extent that doing so does not interfere with the complete and accurate presentation and interpretation of the Trial results. The Trial Center and/or Investigator shall consider such Sponsor's other comments in good faith but has no obligation to incorporate them. If such publication may affect the patentability of any invention to which the Sponsor has rights, the Sponsor shall have the right to request an additional delay to the proposed disclosure of no more than hundred-twenty (120) days so as to allow Sponsor to preserve its intellectual property.

7. APPENDICES

7.1 Adverse Events and Serious Adverse Events: Definitions and Procedures for Recording, Evaluating, Follow-up, and Reporting

Adverse Event Definition

An adverse event (AE) is any untoward medical occurrence (e.g., symptom, sign, diagnosis, or diagnostic test finding) in a patient enrolled into a clinical trial regardless of its causal relationship to trial drug. 
NOTE: An AE can therefore be any unfavorable and unintended sign (including an abnormal laboratory finding), symptom, or disease (new or exacerbated).

Events Meeting the Adverse Event Definition

Any abnormal laboratory test results (hematology, clinical chemistry, or urinalysis) or other safety assessments (e.g., electrocardiogram [ECG], radiological scans, vital signs measurements), including those that worsen from baseline, considered clinically significant in the medical and scientific judgment of the Investigator (i.e., not related to progression of underlying disease).Exacerbation of a chronic or intermittent pre-existing condition including either an increase in frequency and/or intensity of the condition.New conditions detected or diagnosed after trial drug administration even though it may have been present before the start of the trial.Signs, symptoms, or the clinical sequelae of a suspected drug-drug interaction.Signs, symptoms, or the clinical sequelae of a suspected overdose of either trial drug or a concomitant medication.

Events NOT Meeting the Adverse Event Definition

Medical or surgical procedure (e.g., endoscopy, appendectomy): the condition that leads to the procedure is the AE.Situations in which an untoward medical occurrence did not occur (social and/or convenience admission to a hospital).Anticipated day-to-day fluctuations of pre-existing disease(s) or condition(s) present or detected at the start of the trial that do not worsen.

Treatment Emergent Adverse Event Definition

A treatment emergent adverse event (TEAE) is defined as any event not present before exposure to trial drug or any event already present that worsens in either intensity or frequency after exposure to trial drug up to 14 days after last drug exposure.

Definition of Serious Adverse Event

An SAE is defined as any untoward medical occurrence that, at any dose:

Results in death


Is immediately life-threatening
 
The term 'life-threatening' in the definition of 'serious' refers to an event in which the patient was at risk of death at the time of the event. It does not refer to an event, which hypothetically might have caused death, if it were more severe.

Requires inpatient hospitalization or prolongation of existing hospitalization

In general, hospitalization signifies that the patient has been detained (usually involving at least an overnight stay) at the hospital or emergency ward for observation and/or treatment that would not have been appropriate in the physician's office or outpatient setting. Complications that occur during hospitalization are AE. If a complication prolongs hospitalization or fulfills any other serious criteria, the event is serious. When in doubt as to whether "hospitalization" occurred or was necessary, the AE must be considered serious.

Hospitalization for elective treatment of a pre-existing condition that did not worsen from baseline is not considered an AE.

Results in persistent disability/incapacity

The term disability means a substantial disruption of a person's ability to conduct normal life functions.

This definition is not intended to include experiences of relatively minor medical significance such as uncomplicated headache, nausea, vomiting, diarrhea, influenza, and accidental trauma (e.g., sprained ankle) which may interfere with or prevent everyday life functions but do not constitute a substantial disruption.

Is a congenital anomaly/birth defect

Other situations

Important medical events that may not result in death, be life-threatening, or require hospitalization may be considered SAEs when, based upon appropriate medical judgment, they may jeopardize the patient or may require medical or surgical intervention to prevent one of the outcomes listed in this definition.

Medical or scientific judgment must be exercised in deciding whether SAE reporting is appropriate in other situations such as important medical events that may not be immediately life-threatening or result in death or hospitalization but may jeopardize the patient or may require medical or surgical intervention to prevent one of the other outcomes listed in the above definition. These events should usually be considered serious.

Examples of such events include invasive or malignant cancers, intensive treatment in an emergency room or at home for allergic bronchospasm, blood dyscrasias or convulsions that do not result in hospitalization, or development of drug dependency or drug abuse.

Assessment of Severity

The severity of an AE refers to the extent to which an AE affects the patient's daily activities. The Investigator will assess severity for each AE and SAE reported during the trial and assign it to one of the following categories:

- Mild: An event that is easily tolerated by the patient, causing minimal discomfort and not interfering with everyday activities.
- Moderate: An event that causes sufficient discomfort and interferes with normal everyday activities.
- Severe: An event that prevents normal everyday activities. An AE that is assessed as severe must not be confused with an SAE. Severe is a category utilized for rating the intensity of an event; and both AE and SAE can be assessed as severe.

An event is defined as 'serious' when it meets at least one of the predefined outcomes as described in the definition of an SAE, NOT when it is rated as severe.

When changes in the severity of an AE occur more frequently than once a day, the maximum severity for the event must be noted for that day. Any change in severity of signs and symptoms over a number of days will be captured by recording a new AE, with the amended severity grade and the date (and time, if known) of the change. Changes in the severity of an AE must be documented to allow an assessment of the duration of the event at each level of intensity to be performed.

Assessment of Causality

- The Investigator is obligated to assess the relationship between trial drug and each occurrence of each AE/SAE.
- A "reasonable possibility" of a relationship conveys that there are facts, evidence, and/or arguments to suggest a causal relationship, rather than a relationship cannot be ruled out.

- The Investigator will use clinical judgment to determine the relationship.
- Alternative causes, such as underlying disease(s), concomitant therapy, and other risk factors, as well as the temporal relationship of the event to trial drug administration will be considered and investigated.
- For each AE/SAE, the Investigator **must** document in the medical notes that he/she has reviewed the AE/SAE and has provided an assessment of causality.
- There may be situations in which an SAE has occurred, and the Investigator has minimal information to include in the initial report to the Sponsor or its designee. However, **it is very important that the Investigator always assesses causality for every event before the initial transmission of the SAE data to the Sponsor or its designee.**
- The Investigator may change his/her opinion of causality considering follow-up information and send an SAE follow-up report with the updated causality assessment.

The causality assessment is one of the criteria used when determining regulatory reporting requirements.

- The relationship or association of the trial drug in causing or contributing to the AE will be characterized using the following classification and criteria:

Unrelated: This relationship suggests that there is no association between the trial drug and the reported event.

Possible: This relationship suggests that treatment with the trial drug caused or contributed to the AE; i.e., the event follows a reasonable temporal sequence from the time of drug administration or follows a known response pattern to the trial drug but could also have been produced by other factors.

Probable: This relationship suggests that a reasonable temporal sequence of the event with trial drug administration exists and based upon the known pharmacological action of the trial drug, known or previously reported adverse reactions to the trial drug or class of drugs, or judgment based on the Investigator's clinical experience, the association of the event with the trial drug seems likely. The event disappears or decreases on cessation or reduction of the dose of trial drug.

Definite: This relationship suggests that a definite causal relationship exists between trial drug administration and the AE, and other conditions (concurrent illness, progression/expression of disease state, or concurrent medication reaction) do not appear to explain the event. The event reappears or worsens if the trial drug is re-administered.

Recording and Follow-up of Adverse Events and Serious Adverse Event

AE and SAE Recording

- When an AE/SAE occurs, it is the responsibility of the Investigator to review all documentation (e.g., hospital progress notes, laboratory, and diagnostics reports) related to the event.
- The Investigator will then record all relevant AE/SAE information in accordance with this trial's safety reporting documentation.
- It is **not** acceptable for the Investigator to send photocopies of the patient's medical records to the Sponsor or its designee in lieu of completion of the AE/SAE documentation.
- There may be instances when copies of medical records for certain cases are requested by the Sponsor or its designee. In this case, all patient identifiers, except for the patient number, will be blinded on the copies of the medical records before submission to the Sponsor or its designee.
- The Investigator will attempt to establish a diagnosis of the event based on signs, symptoms, and/or other clinical information. In such cases, the diagnosis (not the individual signs/symptoms or related procedure), as well as indication for the procedure, will be documented as the AE/SAE.

- All AEs must be reported in detail on the appropriate page of the eCRF.
- Follow-up of AEs will continue until resolution, stabilization, or death. In case of ongoing aEs at the moment of database closure, the data obtained at the moment of database closure will be used in the statistical analysis. The follow-up of the AE will be documented in the source documents and will be described in the final report only if considered relevant by the Principal Investigator.
- SAEs will be collected from Screening until the final trial visit. SAEs that are related to the investigational drug and continue beyond the normal collection period (i.e., are ongoing at the time a patient exits the trial) will be followed until resolution or until stabilized with sequelae. SAEs that begin after the patient's participation in the trial is complete, but that the Principal Investigator considers to be related to trial medication, may be reported at any time.
- The Principal Investigator or clinical site personnel should notify the Sponsor via email ([contact]) or [contact]) regardless of relationship to the investigational drug, within 24 hours of clinical site personnel becoming aware of the event. The Principal Investigator will provide the initial notification by forwarding a completed "SAE Notification Form" or the relevant, which must include the Principal Investigator's assessment of the relationship of the event to investigational drug.
- New or updated information will be recorded in the originally completed eCRF.
- The Investigator will submit any updated SAE data to the Sponsor or its designee within 24 hours of receipt of the information.
- The Sponsor or its designee will review each SAE report and the Sponsor, or its designee will evaluate the seriousness and the causal relationship of the event to trial drug. In addition, the Sponsor or its designee will evaluate the expectedness according to the IB. Based on the Investigator and Sponsor's assessment of the event, a decision will be made concerning the need for further action.
- The Sponsor or its designee will be responsible for all information processing and reporting according to local legal requirements.
- Contacts and instructions for SAE reporting can be found in the trial's safety reporting documentation.

Suspected Unexpected Serious Adverse Reactions (SUSARs)

Any AE that is serious, associated with the use of the trial drug, and unexpected, i.e., not listed in current IB as expected for this trial (SUSAR), has additional reporting requirements, as described below.

- If the SUSAR is fatal or life-threatening, associated with trial drug, and unexpected, regulatory authorities and IRBs/IECs will be notified within 7 calendar days after the Sponsor, or its designee learns of the event. Additional follow-up (cause of death, autopsy report, and hospital report) information must be reported within an additional 8 days (15 days total).
- If the SUSAR is not fatal or life-threatening but is otherwise serious, associated with trial drug, and unexpected, regulatory authorities and IRBs/IECs will be notified within 15 calendar days after the Sponsor or its designee learns of the event.

The Sponsor or its designee will notify the Investigators in a timely fashion of relevant information about SUSARs that could adversely affect the safety of patients. Follow-up information may be submitted if necessary.

The Sponsor will also provide annual safety updates to the regulatory authorities and IRBs/IECs responsible for the trial. These updates will include information on SUSARs and other relevant safety findings.

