3.5.2.6 Clinical Safety Laboratory

Blood samples for clinical laboratory assessments will be collected at screening, day 1, and day 10, and analyzed locally according to the procedures of the trial center.

The following parameters will be measured:

Clinical chemistry (serum quantitatively):

total bilirubin, gamma glutamyl transferase (gamma-GT), aspartate aminotransferase (AST) (serum glutamic-oxaloacetic transaminase [SGOT]), alanine aminotransferase (ALT) (serum glutamic-pyruvic transaminase [SGPT]), lactate dehydrogenase (LDH), creatinine, blood urea, total protein (albumin and total), inorganic phosphate, sodium, potassium, calcium, glucose.

Hematology (blood quantitatively):

leucocytes, erythrocytes, hemoglobin, hematocrit, thrombocytes, partial automated differentiation: lymphocytes, monocytes, eosinophils, basophils, neutrophils, mean corpuscular volume (MCV), mean corpuscular hemoglobin (MCH), mean corpuscular hemoglobin concentration (MCHC).

Urinalysis (urine qualitatively):

hemoglobin, urobilinogen, ketones, glucose, protein.

In the event of unexplained or unexpected clinical laboratory test values, the test(s) will be repeated as soon as possible and followed up until the results have returned to the normal range and/or an adequate explanation for the abnormality is found. The clinical laboratory will clearly mark all laboratory test values that are outside the normal range and the Principal Investigator will indicate which of these deviations are clinically significant. These clinically significant deviating laboratory results will then be recorded as AEs and the relationship to the treatment will be indicated (see also Appendix 7.1).

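### Appendix 7.1 makes the cause of an abnormal test result a condition for recording it as an adverse event, in conflict with its own definition and, for laboratory results, with Section 3.5.2.6

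*Protocol*

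**What the plan says.** Appendix 7.1 opens with a broad definition. An AE is an untoward occurrence, findings from diagnostic tests included, "in a patient enrolled into a clinical trial regardless of its causal relationship to trial drug". The note beneath it covers "any unfavorable and unintended sign (including an abnormal laboratory finding), symptom, or disease (new or exacerbated".

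The list of events that meet the definition then narrows this for test results. Abnormal laboratory values and other safety assessments (the examples are ECG, imaging and vital signs) qualify when "considered clinically significant in the medical and scientific judgment of the Investigator (i.e., not related to progression of underlying disease". The next bullet of that list includes "Exacerbation of a chronic or intermittent pre-existing condition including either an increase in frequency and/or intensity of the condition".

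The list of events that do not meet the definition has no entry for disease progression. Its nearest entry is "Anticipated day-to-day fluctuations of pre-existing disease(s) or condition(s) present or detected at the start of the trial that do not worsen".

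Section 3.5.2.6 has its own rule for the safety laboratory. Out-of-range values are flagged and "the Principal Investigator will indicate which of these deviations are clinically significant". It continues: "These clinically significant deviating laboratory results will then be recorded as AEs and the relationship to the treatment will be indicated". The section carries no exception for disease-related values. It refers the reader to Appendix 7.1.

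Under Assessment of Causality, Appendix 7.1 states: "The Investigator is obligated to assess the relationship between trial drug and each occurrence of each AE/SAE". Underlying disease appears there among the alternative causes to consider.

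**The concern.** The abbreviation i.e. introduces a restatement. The bullet therefore does not say that a result must matter clinically and also be unrelated to disease. It says that being clinically significant means being unrelated to disease progression. A question of importance becomes a question of cause, and it is answered before an AE exists. The causality duty attaches to AEs, so a result stopped at this point receives no relationship rating.

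The order of these two judgements matters in this trial. Both arms receive ilofotase alfa and there is no untreated arm (Section 3.1.1). The trial is open label for patients, clinicians and staff (Section 3.3.10). Calcium and inorganic phosphate are in the safety panel, and calcium and phosphorus also appear among the pharmacodynamic measurements in the synopsis. Whether a shift in such a value reflects HPP or the drug is what the relationship rating is meant to record. If the answer decides whether the result is recorded at all, the AE tables and listing no longer show that the question arose. Safety is a stated exploratory objective, and the rationale presents the trial as a pilot for a possible Phase 2/3 trial.

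**Working it through.** No formula applies, because the point concerns a recording rule. The check follows one hypothetical finding through each rule: a calcium value outside the normal range on day 10 that the investigator considers clinically important and attributes to HPP progression.

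| Rule | Is it recorded as an AE? |
|---|---|
| Appendix 7.1, general definition and note | Yes, if untoward; cause is irrelevant |
| Appendix 7.1, abnormal-result bullet with the gloss | Not under this bullet, if read literally |
| Appendix 7.1, exacerbation bullet | Yes, if seen as worsening of the pre-existing condition |
| Appendix 7.1, list of events not meeting the definition | Not excluded; the nearest entry covers only expected fluctuation without worsening |
| Section 3.5.2.6 | Yes, with a relationship rating |
| Appendix 7.1, causality step | Presumes that it is recorded; HPP is then weighed as an alternative cause |

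1. **Conflict within Appendix 7.1.** The abnormal-result bullet is the only rule that depends on disease attribution before recording. The general definition ignores cause, and the causality step considers underlying disease after recording.

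2. **Conflict with Section 3.5.2.6.** The same value is an AE there and falls outside the abnormal-result bullet. The cross-reference to Appendix 7.1 does not settle precedence, and no other text does.

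3. **Reach of that conflict.** Section 3.5.2.6 covers laboratory results only. For a vital-sign or ECG finding, the conflict is with the general AE definitions in Section 3.5.2.1 and Appendix 7.1. Section 3.5.2.3 schedules an ECG at screening only, so ECG worsening after dosing can be found only if an extra ECG is taken on clinical indication.

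4. **Direction.** Read as a restriction, the gloss can take results out of the AE set and cannot add any.

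5. **Size.** The protocol gives no rate of laboratory deviations and no rate of attribution to HPP, so an expected loss cannot be computed. The planned arm size gives only a scale: with 6 patients per arm, one patient is 1/6 = 16.7 percentage points of an arm's patient incidence. Omitting an event moves the figure by that amount only if the patient has no other event in the same table row. If the patient has another, only the event count falls. Section 3.6.2.5 plans both counts.

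**The case against.** The strongest reply is that the gloss is one entry in an inclusive list and not an exclusion rule. The general definition, its note and the exacerbation bullet all still reach worsening of HPP, and the list of non-qualifying events does not remove it. A reader might infer that a result attributed to HPP is never an AE and never receives a causality rating. The documents do not support that, because these other rules can still bring it in. This part of the reply stands.

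A second reply is that Section 3.5.2.6 already gives the desired rule for laboratory values. That is correct, but the section sends the reader to the appendix, where the bullet about test results says something different. The exacerbation bullet speaks of a condition, so a symptom-free calcium or phosphate deviation would most naturally be judged under the bullet carrying the gloss.

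A third reply is that little would be lost:

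- Unexplained or unexpected laboratory values are repeated and followed up (Section 3.5.2.6).
- Vital signs are listed (Section 3.6.2.6).
- Summaries of laboratory change from baseline are planned (Section 3.6.2.9), though only where judged clinically useful.
- The definition of a serious adverse event does not contain the gloss, and the sponsor also evaluates causality for each serious report.
- A deviation attributed to HPP might be rated unrelated in any case, and so be absent from the treatment-related table under either rule.

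These points limit the consequence mainly to non-serious abnormal results and to the overall AE tables and listing. They do not remove the contradiction. Follow-up after a single dose is also only 14 days, and nothing in the protocol indicates how often a deviation in that time would be put down to progression.

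**Conclusion.** The protocol is wrong as written on this point. The parenthesis makes the absence of attribution to HPP progression a condition for treating an abnormal test result as an AE. That contradicts the appendix's own definition, its exacerbation bullet and its causality step. For laboratory results, it also contradicts Section 3.5.2.6. The effect on AE counts can only be downward, and its size cannot be computed from the protocol.

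Two further inferences should be avoided. The conflict with Section 3.5.2.6 does not extend to ECG or vital signs, which that section does not cover. The 17-point step (1/6) is the weight of one patient in an arm of six. It is neither an estimate of bias nor the effect of every omitted event.

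The conclusion assumes that at least some investigators would apply the bullet literally, as a restriction. Its practical weight depends on how often deviations would be attributed to HPP, which is unknown. Safety is an exploratory objective reported descriptively, so no formal test is affected.

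**What to change.** Reconcile the passages by deleting the parenthesis from the abnormal-result bullet in Appendix 7.1, so that the bullet ends at the investigator's judgement of clinical significance. Every clinically significant abnormality is then recorded as an AE, as Section 3.5.2.6 already requires for laboratory results. HPP is considered as an alternative cause in the causality assessment, where Appendix 7.1 already places underlying disease.

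If the aim was to keep expected disease variation out of the AE set, the entry on non-worsening fluctuation in the list of non-qualifying events already does so.

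The change removes one parenthesis and adds no visit or sample. The downside is possibly a few more recorded AEs, some of them rated unrelated.
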